The visual effects interface designed by the SCAD team (Aim 1) will use GRF data as input for the timing of animations in the visual effects game. The current prototype visual effect (Figure 3) is a standalone video file untethered to gait hardware. As part of Aim 2, we will develop the technological solutions needed to synchronize the visual effects interface with real-time GRF data recorded during treadmill walking. To accomplish this aim, [name] and her team at Georgia Institute of Technology will develop a custom real-time biofeedback software program to enable integration of the visual effects animation with gait laboratory hardware (i.e. analog data derived from a force platform). [name] team will conduct pilot tests at P.I. [name]'s motion analysis laboratory. Anterior-posterior GRF analog data recorded from the force platform under the right leg will be streamed into the custom real-time biofeedback software program will input the AGRF data to the visual effects software. Our sub-goals for Aim 2 are listed in table below:

Sub-tasks for Specific Aim 2	
(i) Synchronization and Software Development	(ii) Develop augmented reality (AR) game version
- Develop custom software program to synchronize game interface	- Use head-mounted display to superimpose simplified/minimized version of
with AGRF data recorded during treadmill walking	game onto user's real-world view
- This task will culminate in a game version that will be projected	- Two game versions (AR and non-AR) can cater to different patient preferences
on a 2D display screen during treadmill walking (non-AR)	- Helps expand game applications to over-ground, clinical, community settings
(iii) Game pilot testing	(iv) Develop patient report (training session summary for clinicians)
Test (N=5 able-bodied subjects) to confirm that the timing of game	- Develop training report to summarize pre- and post-session values of gait variables
animations synchronize with a user's gait cycle	(e.g. AGRF, trailing limb angle, step length) for paretic and non-paretic leg
	- Will aid clinicians with documenting training effetcs, planning training progression

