Methods for evaluation on stroke survivors: The newly developed games will be tested on 12 individuals with chronic post-stroke hemiparesis and 12 able-bodied adults. Inclusion criteria for stroke participants will include \geq 6-months elapsed since a cortical or subcortical stroke, ability to walk on a treadmill for \geq 2-minutes, ability to communicate with study team, stroke affecting the right leg (to match control participants' biofeedback targeted leg and due to constraints with the game design prototype). Exclusion criteria include orthopedic or neurological conditions preventing walking, neurologic diagnosis other than stroke, cerebellar signs, and cognitive impairments preventing communication during the experiment⁶². Inclusion criteria for able-bodied will be ability to walk, and absence of orthopedic, neurological, or medical conditions that limit walking. Our proposed sample size is based on our studies (N=7 stroke, N=7 able-bodied) where we detected significant increase in targeted leg peak AGRF with power \geq 0.80, with additional participants included to account for the self-report and survey-based game-evaluation outcomes.

Study participants will complete one session comprising exposure to gait biofeedback systems in an order determined by block randomization (3 blocks). Participants will be exposed to 2-3 types of biofeedback interfaces – (i) the AGRF biofeedback game (projector-display, non-VR), and the (ii) traditional, non-game-based, interface (currently used, shown in Figure 2). If we cannot test all 3 gait feedback conditions in 1 session, participants may be asked to complete a 2nd experimental session when 2-3 feedback conditions (and control walk) will be evaluated. In a separate session, some

Outcome variables for Aim 3		
Participant engagement during biofeedback	Hopkins rehabilitation engagement rating scale Pittsburgh rehabilitation participation scale	
Motivation, boredom, and fatigue	10-point visual analog scale Open-ended, non-leading survey questions	
Successful completion of targeted training task	Evaluate success rate (%steps for which target paretic AGRF was achieved)	
Feedback about user experience and game (game ease-of-use, game aesthetics, challenge, ability to understand the game instructions)	10-point scale self-reports Open-ended, non-leading survey questions	
Adverse effects or events	Nausea, dizziness, other negative responses	

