- (ix) Collection of self-report data regarding engagement, adverse effects, challenge, muscle soreness/fatigue during biofeedback: In order to evaluate the feasibility and subject perceptions in response to biofeedback training, we may ask the participant to rate their engagement or motivation, level of challenge encountered during biofeedback, and amount of fatigue on a 0 to 10 visual analog scale. Any other feedback, comments, and adverse effects reported by the subject will also be recorded.
- 3) **Procedures for gait biofeedback:** During biofeedback, auditory and visual biofeedback will be provided using a visual display screen and a speaker pointed

toward the participant. The visual feedback display will vary according to the type of biofeedback interface being evaluated. For the traditional non-game biofeedback, the visual display comprises a horizontal line graph with a moveable cursor that represents the current measured value of antero-posterior ground reaction force for the targeted leg (The MotionMonitor, Innovative Sports Training Inc., Illinois, USA). The targeted peak AGRF range appears as a target line with vertical bars on either end, representing a 6-Newton error-tolerance range centered around the target AGRF³⁹. The auditory feedback comprises an audible "beep" produced every time the cursor entered the target range, i.e. the participant achieves the targeted peak GRF value during their gait cycle^{39, 66}. This same AGRF biofeedback audio-visual system has been successfully used in previous studies in both able-bodied and stroke survivors, showing the feasibility of the biofeedback setup^{39, 66}. For game-based biofeedback, the newly-developed game-based interfaces will be used. The game-based biofeedback may be displayed on a projected screen or with VR goggles.

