For Aim 1 and 2, for preliminary testing of the game design and to get user-feedback on game usability, we plan to collect user-survey and feedback data on 10 stroke survivors and 10 ablebodied individuals. For Aim 3, which is the clinical trial portion of the project, we plan to collect data on a sample of 12 individuals post-stroke and 8 able-bodied neurorehabilitation clinicians.

Inclusion Criteria for Post-Stroke Subjects are: 1) age 30-90 years, 2) chronic stroke (>6 months post stroke) affecting the left leg, 3) ambulatory with or without the use of a cane or walker, 4) able to walk for 2 minutes at the self-selected speed without an orthoses, 5) resting heart rate 40-100 beats per minute.

Exclusion Criteria for Post-Stroke Subjects are: 1) cerebellar signs (ataxic ("drunken") gait or decreased coordination during rapid alternating hand or foot movements, 2) history of lower extremity joint replacement, 3) inability to communicate with investigators, 4) neglect/hemianopia, or unexplained dizziness in last 6 months, 5) neurologic conditions other than stroke, 6) orthopedic problems in the lower limbs or spine (or other medical conditions) that limit walking or cause pain during walking.

Inclusion Criteria for Able-Bodied Individuals are: 1) age 18 to 90 years, 2) no history of neurologic disease, 3) no history of orthopedic disease or injury affecting the lower extremity.

Exclusion Criteria for Able-Bodied Individuals are: 1) history of neurologic disease, 2) history of orthopedic disease or injury to the lower extremity in the past 6 months, 3) pain or discomfort during walking, 4) cardiovascular or medical condition affecting ability to exercise or walk.

Subject Recruitment. Study participants will be recruited from the general community within and outside Emory University.

Withdrawal from study. Participation in the present study will be voluntary and subjects will be able to opt out of the study at any time.

Inclusion of children: Our subject population will be representative of adults with stroke and healthy adults. The incidence of stroke is considered rare in children, estimated to be less than 13 cases per 100,000 children⁷⁰ and their inclusion would not provide additional information compared with the data gathered in adults.

7. Statistical analysis

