Hypotheses testing will be done with a p-value set at 0.05. The primary biomechanical outcome variables will be peak AGRF and trailing limb angle. Secondary variables will be user self-reports regarding game engagement, motivation, and fatigue.

Power Analysis: The current protocol is designed as a preliminary study, and will be used to conduct systematic power analysis, effect-size and sample-size calculation, which will be utilized to design a larger-scale future study.

8. Adverse event reporting

We will record and notify the IRB of any adverse events that occur during the protocol.

10. Device information

Equipment for Motion Analysis and Gait Retraining: A 7-camera system will be used to collect motion analysis data (Vicon, Oxford, UK). Ground reaction forces during treadmill walking will be collected using a treadmill instrumented with two 6-component force platforms under each belt (Bertec, USA). During over ground walking, ground reaction forces will be collected using a force plate embedded within the lab floor (AMTI, USA). In addition, small electromyography (EMG) sensors will be attached to various muscles to collect EMG data (Noraxon Inc., Arizona, USA). The EMG sensors will be attached using hypo-allergenic adhesive. Pressure-sensitive foot switches (25-mm diameter MA-153, Motion Lab Systems, LA) will be attached to the underside of the subjects' shoes; the foot switch data will be used to record gait events (Noraxon Inc, Arizona, USA). All these devices widely used for measurement of human movements.

Equipment for gait biofeedback: The auditory and visual biofeedback will be provided using a visual display projector screen and a speaker pointed toward the participant. The visual feedback display comprises a horizontal line graph with a moveable cursor that represents the current measured value of antero-posterior ground reaction force for the right leg. The biofeedback software is a plugin provided by The MotionMonitor, Innovative Sports Training Inc., Illinois, USA. The game-based biofeedback interfaced will be designed and developed as part of this current project, with help from our collaborators at Savannah College of Arts and Design (SCAD) and Georgia Institute of Technology. We may use a commercial off-the-shelf VR headset such as the Oculus for the VR display.

11. References

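### Section 6 requires a stroke affecting the left leg and the Aim 3 methods require one affecting the right, so no hemiparetic Aim 3 participant can meet both criteria.

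*Combined protocol and SAP*

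**What the plan says.** Section 6 (Participant selection) opens with the samples for all three aims. It says "For Aim 3, which is the clinical trial portion of the project, we plan to collect data on a sample of 12 individuals" post-stroke, and then gives one list of inclusion criteria for post-stroke subjects. That list is not limited to any aim. Its second item is "chronic stroke (>6 months post stroke) affecting the left leg".

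Section 5, Specific Aim 3 (methods for evaluation on stroke survivors), says the games "will be tested on 12 individuals with chronic post-stroke hemiparesis and 12 able-bodied adults". Its own inclusion criteria contain "stroke affecting the right leg". Two reasons are given: a match with the controls' "biofeedback targeted leg and due to constraints with the game design prototype".

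Other places bear on which leg drives the feedback:

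- **Section 5, Aim 2 methods:** "Anterior-posterior GRF analog data recorded from the force platform under the right leg will be streamed" into the biofeedback software. The Aim 1 description of the prototype also takes right-leg force as its input.
- **Section 10, equipment for gait biofeedback:** the display shows "the current measured value of antero-posterior ground reaction force for the right leg".
- **Section 5, procedures for gait biofeedback:** the conventional display shows "the current measured value of antero-posterior ground reaction force for the targeted leg".
- **Section 5, procedures for gait analysis:** in stroke participants the targeted leg is the paretic one, with no side named. In able-bodied participants it may be either leg.
- **Section 5, Specific Aim 3:** the scripted instruction and the force target both refer to the paretic leg.

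**The concern.** These are two operative inclusion criteria for the same people, and they are direct opposites. The lists differ in other ways too. Section 6 adds an age range and a resting heart rate range, for example, but a participant can satisfy both lists on those items. On the side of the stroke that is impossible.

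The immediate consequence is for screening. Staff cannot apply both lists, every stroke enrolment in Aim 3 departs from one written criterion, and a reader of the results could not tell from the protocol which population was intended.

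A second consequence is conditional. Suppose left-paretic participants were enrolled under Section 6 and the right-leg signal were used as the Aim 2 methods and Section 10 describe. The feedback would then come from the non-paretic leg, although the intervention is meant to train the paretic leg. This does not arise if the targeted-leg wording in the gait procedures is followed.

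**Working it through.** The check is one of logic. No sample-size figure has to be reproduced: the plan gives no effect size or standard deviation from which its 12 could be recomputed, and the point does not depend on them.

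**Inputs**

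- Number of Aim 3 stroke participants: 12, hemiparetic (Section 5, Specific Aim 3; Section 6).
- Side required by Section 6: left.
- Side required by the Aim 3 methods: right.
- Each participant has one paretic and one non-paretic leg, as the protocol assumes throughout.

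**Step 1: do both lists govern the same people?** Section 6 names the Aim 3 sample of 12 and follows it with a single stroke list. The Aim 3 methods name 12 people with chronic hemiparesis and give their own list. No sentence assigns the two lists to different phases.

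**Step 2: can both be met?** The set of sides allowed by both is {left} ∩ {right} = ∅. The number of hemiparetic participants who can satisfy both is therefore 0 of 12.

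**Step 3: how many breach one list?** Let k of the 12 be left-paretic and 12 − k right-paretic.

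- Breaches of the Aim 3 criterion (right required) = k.
- Breaches of the Section 6 criterion (left required) = 12 − k.
- Total = k + (12 − k) = 12.

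| k (left-paretic) | Breach Aim 3 methods | Breach Section 6 | Total |
|---|---|---|---|
| 0 | 0 | 12 | 12 |
| 6 | 6 | 6 | 12 |
| 12 | 12 | 0 | 12 |

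The total is 12 for every k from 0 to 12.

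**Step 4: does the side matter for the feedback?** Compare the right-leg wording (Aim 1 prototype, Aim 2 methods, Section 10) with the paretic or targeted-leg wording (Aim 3 instruction and target, gait analysis procedures, biofeedback procedures).

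- Right-paretic participant: the right leg is the paretic leg, and all of these statements agree.
- Left-paretic participant: the right leg is the non-paretic leg, and the two groups of statements conflict.

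The leg wording is therefore consistent for stroke participants under the Aim 3 criterion and inconsistent under the Section 6 criterion.

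**Step 5: would the primary measurement be lost?** No. Each treadmill belt has its own force platform, so force is recorded from both legs and paretic peak AGRF could still be measured. Only the feedback delivered would be affected. How likely that is cannot be derived from the documents, so it is left unquantified.

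**The case against.** The strongest reply is that this looks like a one-word drafting slip. The Aim 3 criterion comes with two reasons, and right-leg wording recurs in the Aim 1, Aim 2 and equipment text. The left-leg criterion appears once and without a reason. That pattern is real, but it does not prove which sentence is the error. The left-leg wording stands in the formal selection section, from which staff would be expected to screen.

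A second reply is that no harm to the comparison has been shown. The interfaces are compared within participants in randomised order, the targeted leg is the paretic one on either side, both legs are recorded, side of hemiparesis is collected, and the study calls itself preliminary. This is fair as far as it goes: no effect on type I error, power or safety is claimed here. The point rests on eligibility criteria that cannot both be followed.

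Third, the 12-of-12 count is trivial, because it would hold for any sample size. That is correct. It shows that the contradiction is complete and does not measure harm. Nor is recruitment impossible, since a site using one list could enrol 12.

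Fourth, the Aim 2 sentence describes development work and need not fix the leg streamed in Aim 3 sessions. The wording of the biofeedback procedures is already neutral as to side. Both observations stand, and they limit how much text needs editing. A further possible defence is that the protocol allows phase 1 experience to influence phase 2. That statement names no eligible side and withdraws neither criterion.

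**Conclusion.** The concern holds and must be fixed. The two side criteria exclude each other: 0 of 12 hemiparetic Aim 3 participants can meet both, and 12 of 12 breach one. The conclusion assumes only that each participant has a single paretic leg, which is how the protocol treats them; a person with both legs affected would be the sole exception. The documents do not settle which side is intended, and none is chosen here. The possible delivery of feedback from the non-paretic leg is a conditional and unquantified consequence, and the conclusion does not rest on it.

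**What to change.** - State one eligible side, in identical terms, in Section 6 and in the Specific Aim 3 methods. The sponsor must say which side is intended, and it must agree with the leg streamed to both the game and the conventional display.
- Check the remaining leg wording against that statement and edit only what disagrees: the Aim 2 methods, the gait analysis procedures (where the choice of either leg for able-bodied participants sits awkwardly with the control-matching reason in Aim 3), the biofeedback procedures and Section 10.
- If the Section 6 side is confirmed, also explain how the game-prototype constraint cited in the Aim 3 methods is overcome.
- Optionally, at set-up, compare the recorded side of hemiparesis with the force platform being streamed.

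The cost is text only, apart from whatever work the prototype constraint would need if the Section 6 side is confirmed. No extra participants, visits or data fields are required, since side of hemiparesis is already among the information collected.
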